2.2 INTERNAL PILOT

An 18-month internal pilot study will be conducted to ensure recruitment targets are realistic and the targets for recruitment are achievable. This will comprise three phases (site initiation and early recruitment, nested qualitative study (known as the Quintet Recruitment Study) and main internal pilot phase).

At the end of the internal pilot phase (at 18-months), the number of sites open to recruitment, recruitment rates and adherence to allocated treatments will be assessed. Red, amber and green outcomes will be set for recruitment, site opening and data completion (please see section on planned recruitment for further details.)

Quintet Recruitment Intervention (QRI) Sub-study – Qualitative research to optimise recruitment

Objectives:

The aim of the QRI is to work with EARNEST trial clinical research teams to understand the recruitment process in the early stages, so that any difficulties related to design or conduct can be raised and changes put in place. Specifically:

- To determine any training that needs to be developed, or feedback given to members of the clinical care team approaching and recruiting patients and ensure inclusivity.
- To determine any modifications in patient-facing materials that would improve the inclusivity of patient recruitment.

Primary outcome:

More than half of eligible patients with uTBAD accept randomisation.

Secondary outcome.

• To increase (by 10%) the representation of patients of diverse ethnic, socioeconomic and educational backgrounds in the trial.

Patients for this study will be recruited during the screening phase at selected sites. The Quintet Recruitment Intervention (QRI) [15, 16] will be used for semi-structured interviews (see Appendix 4 for script guide), with individuals involved in screening and presenting EARNEST to patients, will take place across all sites (n=5-10 per site).

Confidential Page 21 of 30

EARNEST	Protocol No: 174766	Sponsor: London	Imperial	College	V1.0 7 th Oct 2024

Interviews with patients who decline randomisation will also be used to explore whether the patient information sheet or decision aid could be modified to enhance patient recruitment (script guide in Appendix 4). Interviews will be conducted by the University of Leicester EARNEST trial QRI team Interviews may be carried out on the telephone or via video conferencing for some participants. They will be recorded digitally and analysed following the conventions of thematic and the constant comparison approach. Summaries of pseudo- anonymised findings will be presented to EARNEST principal investigators and to the TMG, including supporting evidence to describe factors hindering recruitment. A potential plan of action to improve recruitment will be proposed to facilitate decision making and define responsibilities for implementation.

3. PARTICIPANT ENTRY

3.1 Study setting and population

(i) Inclusion criteria

- Patients with uTBAD, 10 days-3 months after the day of admission with acute uTBAD to hospital (the date of the index event).
 - o Notes:
 - patients are allowed left subclavian artery coverage/bypass and/or adjunctive procedures on/to the iliac vessels to permit safe introduction of the delivery device.
 - Stenting must be planned to occur within 3 months after index event
- Age ≥18.
- Life expectancy ≥2 years.
- Discharged from high dependency/critical care and not receiving opiate analgesia or similar sedatives for at least 48 hours before enrolment.
- Willing and able to provide written informed consent: voluntary agreement to participate in the trial following full disclosure of risks and procedures required.

(ii) Exclusion criteria

- Complicated TBAD (ruptured aorta, aortic dilatation >5cm or visceral/limb/spinal malperfusion, persistent pain or uncontrolled BP)
- Known connective tissue disorder
- Previous TBAD
- Type A dissection with distal residual dissection
- Intramural haematoma alone

Confidential Page 22 of 30

EARNEST	Protocol No: 174766	Sponsor: London	Imperial	College	V1.0 7 th Oct 2024

- Traumatic dissection
- Aorto-iliac aneurysms
- Requiring carotid/innominate artery revascularisation to create a TEVAR landing zone or planned visceral artery intervention
- Unable to attend follow-up appointments
- Pregnancy during the period where stenting of the aorta would be necessary.
- Participation in any other interventional clinical trial.

There will be no patient excluded as a result of sex, geographical location, disability, gender, marriage and civil partnership status, ethnicity, religion or belief, sexual orientation, socioeconomic status or access to health or social care. There will be no exclusion of patients who suffer a uTBAD during pregnancy and maternity, although the mother cannot undergo the procedure whilst pregnant as there will be significant radiation risks to the child.

4. PROCEDURES AND MEASUREMENTS

4.1 Identification and recruitment of participants

Patients with uTBAD will be invited to take part in the trial once the requirement for intensive care or high dependency care has ended and the patient has not received opiate analgesia for at least 48 hours. Recruitment may occur in NHS hospitals in the UK when patients are:

- At the hospital before discharge
- In the outpatient setting at review after admission for uTBAD

Trial centres will be vascular hubs/centres able to deliver BMT+SURV and TEVAR+BMT+SURV arms of the study for uTBAD patients. Spoke acute NHS hospitals will be effective patient identification centres. Participants will be identified by vascular surgeons, cardiologists, cardiac surgeons, research nurses and physicians at vascular units acting as principal trial centres. There is no payment for taking part in this study. The researchers won't receive any personal payment over and above normal salary, or any other benefits or incentives.

4.2 Screening and pre-randomisation evaluations

There is no test required before the patient enters the trial. Potential participants will be screened to determine whether they meet all the inclusion criteria and none of the exclusion criteria listed for the trial. Sites will be asked to capture patient initials of each identified patient and to record the reasons for ineligibility (including whether complicated, uncomplicated and stented outside of trial) or for non-participation to help inform study progress.

Potential participants will be given information on the trial by local research staff when appropriate (which may be <10 days after their acute uTBAD or after discharge) and

Confidential Page 23 of 30

EARNEST	Protocol No: 174766	Sponsor: London	Imperial	College	V1.0 7 th Oct 2024

consented at or after 10 days. Each potential participant will be given a copy of the patient information sheet (PIS) and informed consent form (ICF). potential participants will be given at least 24 hours to read the PIS and consider their participation.

The consent may only take place once the index admission requirement for intensive care or high dependency care has ended, and the patient has not received opiate analgesia for at least 48 hours. Informed consent must be obtained before any study procedures are performed. After consent, participant baseline assessments can be performed and eligibility can be confirmed. Sites will make provisions for translation during the consent process so that the process can take place in the participants native language.

4.3 Randomisation and Blinding

Randomisation: 470 participants will be allocated to treatment group (1:1) by minimisation, which assigns the next patient to the group that balances the main prognostic factors (e.g., age, sex, centre) with high probability (e.g., 75%). This will be generated by computer algorithm and released after checking patient eligibility and written consent. This will be implemented by a validated web-based system Sealed Envelope. Once a participant is confirmed to be eligible for randomisation, qualified site staff will register the participant on the system and randomise them. A participant ID will be generated which must be used to identify participants on CRFs from this point.

Blinding: For ethical and practical reasons, participants and clinicians cannot be blinded to treatment allocation. However, endpoints will be adjudicated by an expert panel (PROBE study - Prospective Randomized Open, Blinded End-point).[18]

4.4 Visit Schedule

Visit	0	1	2	3	4	5-9
	Screening	Consent	FOR TEVAR+BMT+ SURV only TEVAR Intervention	Clinical and research assessment	Clinical and research assessment	Clinical and research assessment
TIMEPOINT	Within 3 months of index uTBAD	After the requirement for intensive care or high dependency care has ended, and the patient has not received opiate analgesia for at least 48 hours and from 10 days to 3 months of	10 days-3 months after index uTBAD	FOR BMT+SURV 6 weeks after discharge from hospital admission for the index event c (±14 days) FOR TEVAR+BMT+ SURV	6 months after randomisation (±30 days)	1 year and yearly to 5 years after randomisation. (±30 days)

Confidential Page 24 of 30

EARNEST	Protocol No:	Sponsor:	Imperial	College	V1.0 7 th Oct 2024
	174766	London			

		II.		Į.		
		index uTBAD, noting TEVAR must be performed in 3 months after index event		6 weeks after TEVAR ^c (±14 days)		
Inclusion & exclusion criteria	Х	X				
Informed consent		x				
Demography		X				
Medical history		X		X	x	x
Clinical assessment		x		x	x	x
Clinical details of uTBAD admission		x				
Blood pressure ^a		x	x	x	x	x
CTA aorta		Х		Xp		X
Site report of CT Aorta		X		X		X
Transfer of CT to core lab		X		X (six weeks after discharge from hospital after index event OR six weeks after TEVAR)		X, at 1 and 5 years only
EQ-5D-5L		X		x, measured before imaging results are relayed to the participant	x, measured before imaging results are relayed to the participant	x, measured before imaging results are relayed to the participant
Procedural details			X			
Health resource use, from NHS and personal and social care				x	x	х
Document re- intervention				X	X	x
Document adverse events			X	X	X	х

Confidential Page 25 of 30

EARNEST	Protocol No: 174766	Sponsor: London	Imperial	College	V1.0 7 th Oct 2024

^aStandardised BP measurement: This will be measured using standard protocols. At each visit, three BP recordings will be measured in the sitting position using a validated semi-automated device after at least ten minutes rest. The mean of the second and third readings will be used in analyses. Smoking or vaping will not be permitted for 30 minutes before BP measurement.

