All patients will be seen at 6-weeks, 6-months, one year and yearly (to five years after enrolment) when clinical and cost-effectiveness data will be collected. Both groups will undergo CT/MRI assessment at one year and yearly (to five years after enrolment).

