4.5 Follow-up

Follow up visits will take place at each of the sites in a clinical examination room for interview, examination, BP readings and required questionnaires to be completed. Each study visit will be expected to take less than one hour including rest periods for the subject.

Data will be collected on electronic case report forms using a study database called Sealed Envelope which is a regulatory-compliant database and is sponsor-approved for non-CTIMP studies.

Participants will be consented for the central study team to access routinely collected healthcare data, confirming whether the patient has had additional procedures/hospital admissions during the follow up period. Consent will also allow for identifiable data to be linked with the national databases including the National Vascular Registry data, Hospital Episode Statistics data (in England), CHI data, Electronic Data Research and Information Service DRIS (in Scotland) and from the Office of National Statistics. The identifiable fields (NHS number) required for linkage will be encrypted using a one-way encryption algorithm. We will ask patients if they are happy to give consent for their health status to be followed up over time. This will be done by linking the patient's identifiable data with records held by the NHS and maintained by the NHS Information Centre and the NHS Central Register, or any applicable NHS information system. This will allow us to track what happens after the study finishes and observe if anyone gets further tests/investigations and treatment they may have.

As uTBAD may not develop for many years, we will also ask patients to give consent for us to keep personal data stored or accessed for 15 years on the NHSCR (National Health Service Care Register) so that data from national registries can be evaluated. For instance, long-term survival information to be flagged through national registries, for example NHS Digital (previously the Health and Social Care Information Centre); Office of National Statistics (ONS) in England/Wales; General Register Office in Scotland; Hospital Episode Statistics (HES) or Office for Health Improvement & Disparities

Confidential Page 26 of 30

^b If the participant has already undergone a scan at 6 weeks prior to randomization, ie. The patient has been randomised after 6 weeks from discharge, an additional clinical 6 week scan will not be required. All images should however be transferred to the core laboratory

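### The six-week visit runs on a different clock in each arm, so some BMT+SURV participants are randomised after it was due and their six-week scan can pre-date randomisation

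*Protocol*

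**What the plan says.** The table in section 4.4 gives visit 3 two anchors, each ±14 days: "6 weeks after discharge from hospital admission for the index event" for BMT+SURV and "6 weeks after TEVAR" for the TEVAR arm. Visit 3 collects EQ-5D-5L, blood pressure, resource use, re-interventions, adverse events and a CT that goes to the core lab. The later visits share one clock: visit 4 is at "6 months after randomisation (±30 days") and visits 5 to 9 are at "1 year and yearly to 5 years after randomisation. (±30 days").

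The other sections do not agree on the six-week point:

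- Section 1.9 lists six-week quality of life and blood pressure in a series that ends in a reference to randomisation, with no separate clock for week 6.
- Section 2.1 has one visit for everyone ("All patients will be seen at 6-weeks, 6-months, one year and yearly (to five years after enrolment")), but counts the BMT+SURV scan from discharge.
- Section 4.6 counts the scan from hospital discharge in both arms.
- Section 7.3 counts it from TEVAR or from the dissection itself.

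On entry, section 8.9 allows consent from 10 days to 3 months after the index event. Section 4.1 allows recruitment "In the outpatient setting at review after admission for uTBAD". Footnote b to the visit table (printed at the foot of the page that carries section 4.5) covers a participant randomised more than 6 weeks after discharge: "an additional clinical 6 week scan will not be required", and all images still go to the core lab. Section 4.2 bars study procedures before consent.

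**The concern.** A visit used to compare randomised groups should sit at the same distance from randomisation in both. Here one arm is measured at a fixed time after an acute admission and the other at a fixed time after a procedure, and neither time is tied to allocation.

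This has two consequences. First, at week 6 the between-arm contrast mixes treatment with time since the acute illness. Second, a BMT+SURV participant who enters late has no workable visit 3. The scan that stands for it was taken before allocation and cannot show any effect of it, and the questionnaire and clinic items are due on a date before enrolment.

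Three uses are exposed:

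- The six-week EQ-5D value, which enters a mixed model with a constant treatment effect over time (section 7.3) and would ordinarily be a point on the QALY curve.
- The six-week scan, which section 7.3 includes in the core lab's group comparison.
- The pilot progression criterion on completed six-week clinical follow-up (section 7.2).

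**Working it through.** The protocol gives no figure on this point to reproduce. The check is date arithmetic, with day 0 as the index event and 3 months taken as 91.3 days.

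Inputs:

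- Randomisation day R: 10 to 91 (section 8.9).
- TEVAR day T: "10 days-3 months after index uTBAD" (section 4.4), with T at or after R.
- Discharge day D: not given. Assumed 10, with a range of 5 to 28.

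Timing from the index event:

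- BMT+SURV visit 3 = D + 42. With D = 10 this is day 52, with a window from day 38 to day 66. For D from 5 to 28 it is day 47 to day 70.
- TEVAR visit 3 = T + 42, which is day 52 to day 133.
- Gap between arms = T − D. With D = 10 this is 0 to 81 days, and 40 days if T = 50. With D = 28 it is −18 to +63 days.

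Timing from randomisation, D = 10:

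- BMT+SURV: 52 − R, from +42 days (R = 10) to −39 days (R = 91).
- TEVAR: T − R + 42, from +42 days (T = R) to +123 days (R = 10, T = 91).

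The nominal BMT+SURV visit therefore precedes randomisation when R > 52, and its whole window does so when R > 66.

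The share of participants affected depends on when they are randomised, which the protocol does not give. Purely as an illustration, suppose R is uniform over the permitted 81.3 days. The share with the nominal date already past is (91.3 − D − 42)/81.3. The share with the whole window past is (91.3 − D − 56)/81.3. If out-of-window visits do not count as done, the ceiling on pilot completion over both arms is 1 minus half of the second share.

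| D | Nominal date past if R exceeds | Window past if R exceeds | Share of BMT+SURV, nominal | Share, whole window | Completion ceiling |
|---|---|---|---|---|---|
| 5 | 47 | 61 | 54% | 37% | 81% |
| 10 | 52 | 66 | 48% | 31% | 84% |
| 14 | 56 | 70 | 43% | 26% | 87% |
| 21 | 63 | 77 | 35% | 18% | 91% |
| 28 | 70 | 84 | 26% | 9% | 96% |

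The green threshold in section 7.2 is above 85%. With early discharge and this even spread of entry, the trial could miss green even if every site did everything possible.

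What can and cannot pre-date randomisation follows from reading three places together. Footnote b lets an earlier scan stand and sends it to the core lab. Footnote c still calls for a scan after TEVAR, so in practice only BMT+SURV participants can lack an early post-randomisation scan. Section 4.2 means that EQ-5D-5L, blood pressure and resource-use forms cannot exist before consent; for late entrants they are late or missing, and the protocol does not say which.

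**The case against.** The strongest reply is that the two anchors have a purpose. The scan after TEVAR checks stent placement, the BMT+SURV scan follows usual UK surveillance after discharge, and early safety of the procedure is a secondary aim. A randomisation clock has its own price: a participant randomised on day 10 and stented on day 91 would have the six-week assessment on day 52, before the procedure. This stands as a reason to leave the clinical scans alone. It does not explain why the questionnaire and resource-use items should follow them.

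The reach of the problem is also limited. Section 1.9 has costs and blood pressure analysed at 5 years, the remodelling aim in section 1.6 is at 1 year, and visit 3 is one of seven follow-up visits in the EQ-5D model. The day counts at the ends of the range are extremes. Section 8.9 asks that consent leave time for TEVAR, so randomisation near day 91 should be uncommon and the uniform shares are probably too high at the late end. All of this stands.

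A reader might infer that BMT+SURV quality-of-life, blood pressure and cost data are themselves collected before randomisation. The protocol does not support that: only the scan can pre-date it. A reader might also infer that the 5-year cost and blood pressure results are distorted, or that all comparisons before 6 months must be given up. The first does not follow, since later visits share one clock. The second would discard the period in which procedural harm is most likely to show.

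**Conclusion.** The point holds in a limited form. Visit 3 has arm-specific anchors, five sections describe the six-week point in ways that cannot all be followed, and the protocol does not say what happens at visit 3 for BMT+SURV participants randomised after it falls due. For them the core-lab scan can be a pre-allocation image, and the other items are overdue or undeliverable.

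With discharge on day 10 the thresholds are randomisation after day 52 (nominal date) and after day 66 (whole window). They move one for one with discharge day. The proportion affected cannot be known from the protocol; the tabulated shares rest on an assumed uniform entry pattern.

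The damage is confined to the six-week EQ-5D value and what it feeds, the six-week remodelling comparison and the pilot completion criterion. The primary endpoint and the sample size do not depend on visit 3, and results from 6 months on are largely unaffected. An analysis plan cannot fully repair this, because modelling actual dates does not recover an assessment that was never scheduled after randomisation.

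**What to change.** Leave the clinical scans where they are, and reconcile sections 1.9, 2.1, 4.4, 4.6 and 7.3 as follows:

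- Time the research items of visit 3 from randomisation in both arms, at 6 weeks ±14 days (28 to 56 days after randomisation). These are EQ-5D-5L, resource use, adverse events, and blood pressure by the protocol's standard method where a clinic visit takes place. Keep the rule that EQ-5D-5L is completed before imaging results are relayed.
- Class any scan taken before randomisation as baseline, and leave it out of the six-week between-arm remodelling comparison.
- Use actual days since randomisation in the EQ-5D and QALY analyses.
- State how the pilot completion criterion counts BMT+SURV participants randomised after the visit falls due under the present wording. Under a randomisation clock this case no longer arises for the research items.

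The cost is an edit to the schedule table and the matching text, and a short extra contact for participants whose clinic visit does not fall at that time. Some TEVAR participants will be assessed before, or soon after, their procedure; recording the procedure date next to the assessment lets readers see this. The sample size does not change.

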4.5 Follow-up

Follow up visits will take place at each of the sites in a clinical examination room for interview, examination, BP readings and required questionnaires to be completed. Each study visit will be expected to take less than one hour including rest periods for the subject.

Data will be collected on electronic case report forms using a study database called Sealed Envelope which is a regulatory-compliant database and is sponsor-approved for non-CTIMP studies.

Participants will be consented for the central study team to access routinely collected healthcare data, confirming whether the patient has had additional procedures/hospital admissions during the follow up period. Consent will also allow for identifiable data to be linked with the national databases including the National Vascular Registry data, Hospital Episode Statistics data (in England), CHI data, Electronic Data Research and Information Service DRIS (in Scotland) and from the Office of National Statistics. The identifiable fields (NHS number) required for linkage will be encrypted using a one-way encryption algorithm. We will ask patients if they are happy to give consent for their health status to be followed up over time. This will be done by linking the patient's identifiable data with records held by the NHS and maintained by the NHS Information Centre and the NHS Central Register, or any applicable NHS information system. This will allow us to track what happens after the study finishes and observe if anyone gets further tests/investigations and treatment they may have.

As uTBAD may not develop for many years, we will also ask patients to give consent for us to keep personal data stored or accessed for 15 years on the NHSCR (National Health Service Care Register) so that data from national registries can be evaluated. For instance, long-term survival information to be flagged through national registries, for example NHS Digital (previously the Health and Social Care Information Centre); Office of National Statistics (ONS) in England/Wales; General Register Office in Scotland; Hospital Episode Statistics (HES) or Office for Health Improvement & Disparities

Confidential Page 26 of 30

^b If the participant has already undergone a scan at 6 weeks prior to randomization, ie. The patient has been randomised after 6 weeks from discharge, an additional clinical 6 week scan will not be required. All images should however be transferred to the core laboratory

^c Participants allocated to the TEVAR+BMT+SURV group will have a clinical 6 week scan to ensure adequate stent placement.

EARNEST	Protocol No:	Spansari	Imperial	Collogo	V1.0 7 th Oct 2024
EARNEST	174766	Sponsor: London	imperiai	College	V1.0 7 OCI 2024

